### **8.7.2 Lab Based Stopping Rules**

Summaries will be provided using counts and percentages for subjects who meet the stopping rules as described below:

- If ALT or AST increases to  $>5\times$  Reference baseline (and is at least  $> 5x$  ULN)
- If ALT or AST increases to  $>2\times$  Reference baseline (and is at least  $> 3x$  ULN) AND the increase is accompanied by
  - a concomitant total bilirubin increase to  $>2\times$  Reference baseline (and at least  $> 2x$  ULN) OR
  - the INR is concomitantly  $> 1.5$
- If ALT or AST increases to  $>2\times$  Reference baseline (and is at least  $> 3x$  ULN) AND
  - elevations of ALT/AST are accompanied by signs or symptoms of right upper quadrant abdominal pain, anorexia, nausea, vomiting, fever, eosinophilia ( $>$  upper limit of normal of absolute eosinophilia count), and/or rash.

#### **8.7.2.1 Close Monitoring for Drug Discontinuation due to Elevated ALT/AST**

The following close observation guidelines applies to subjects that repeat assessments show persistent elevations of transaminases, but who do not meet drug discontinuation criteria, and for subjects who discontinue study drug due to ALT/AST elevations.

Close monitoring activities will be initiated:

- If ALT or AST increases  $> 2x$  Reference baseline (and is at least  $> 3x$  ULN) OR
- If ALT or AST increases  $> 8x$  ULN (whichever comes first)

Details related close monitoring is available in protocol section 10.2.

A listing will be used to track and evaluate subjects that are part of the close observation guidelines.

### **8.7.3 Clinical laboratory evaluations**

Summaries of clinical laboratory values and change from baseline will be performed using an 8-number summary by visit and treatment group. All subjects in the safety population

## Final Analysis

### Statistical Analysis Plan (SAP)

will be included in these summaries. Baseline is defined as the last value collected prior to first dose of study drug.

The number and percentage of subjects with treatment-emergent laboratory abnormalities until the last dose of study drug will be summarized by treatment group. In addition, shift from baseline tables will be generated by visit and treatment group.

For categorical tests: Treatment-emergent abnormal is defined as a change from normal at baseline to abnormal at any post-baseline visit

For continuous tests:

- Treatment-emergent high is defined as a change from a result less than or equal to the high limit at baseline to a value greater than the high limit at any time post-baseline.

Results will be reported according to any value greater than the high limit, any value greater than 2x ULN and 3x ULN

- Treatment-emergent low is defined as a change from a result greater than or equal to the low limit at baseline to a value less than the low limit at any time post-baseline
- Results will be reported according to any value less than the lower limit, any value less than 2x LLN and 3x LLN.

All summary tables will include the abnormalities that occur during the treatment-free follow-up after the date of last dose. The denominator for these will include any subject who entered into the 4 week treatment-free follow-up phase.

All laboratory data will be included in the data listings and all test values outside the normal range will be flagged as low or high.

Separate listings will be provided for: Pregnancy test, FSH, HIV, HCV, and HBV along with biomarkers for NASH (Cytokeratin (CK)18, GLP-1 (glucagon-like peptide-1)).

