#### Analyses Populations

- *Safety Population (SAF)*: All subjects who receive at least one dose of study drug. Subjects will be included in the treatment group that corresponds to the study drug received during the study.
- *Intent-to-treat (ITT) Population*: ITT subjects will be considered those randomized to treatment. ITT subjects will be analyzed according to the treatment to which they were randomized. In the event the SAF is the same as ITT only the ITT will be reported. This will be the primary efficacy population.
- *Per Protocol (PP) Population*: All randomized and treated subjects that do not have major protocol deviations which could unduly influence the efficacy analysis.
- *Pharmacokinetic Population*: All subjects receiving active study drug and having any measurable plasma concentration of study drug at any time point.

Safety Analyses: Statistical methods for the safety analyses will be primarily descriptive in nature. No formal statistical comparisons of EDP-305 dose levels will be made. Safety data, including AEs, vital signs, ECGs, concomitant medications, and laboratory values will be summarized separately for each treatment group. Change from baseline will be included in summary tables for vital signs, ECG parameters, and laboratory parameters. Shift tables will also be generated for each safety laboratory parameter. All laboratory data will be included in the data listings and all test values outside the normal range will be flagged. Adverse events will be summarized by the Medical Dictionary for Regulatory Activities (MedDRA) system organ class and preferred term by treatment group.

Pruritus Analyses: Descriptive statistics will be provided for patient reported outcomes such as the 5D-itch scale, VAS and other assessments. Observed, change from baseline, and percent change from baseline results will be presented by visit and treatment group. Additional modeling may be performed if data permits. Further analysis of all pruritus assessment tools will be described in detail in the SAP.

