### **11.7.3. Clinical Laboratory Data**

Laboratory assessments will be reported as mean change from baseline across scheduled visits, and as the incidence rate of shift change from baseline. Shift from baseline tables will be generated for each treatment group for selected analytes. Laboratory shifts will be displayed as

treatment-emergent abnormal, high, or low results. The following details the summary types where LLN = Lower limit of the normal range, ULN = Upper limit of the normal range.

For categorical tests: Treatment-emergent abnormal is defined as a change from normal at baseline to abnormal at any postbaseline visit

For continuous tests:

- Treatment-emergent high is defined as a change from a result less than or equal to the high limit at baseline to a value greater than the high limit at any time postbaseline.  
Results will be reported according to any value greater than the high limit, any value greater than 2x ULN and 3x ULN
- Treatment-emergent low is defined as a change from a result greater than or equal to the low limit at baseline to a value less than the low limit at any time postbaseline  
Results will be reported according to any value less than the lower limit, any value less than 2x LLN and 3x LLN.

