## **1 INTRODUCTION**

The Statistical Analysis Plan (SAP) describes the statistical methods to be used during the reporting and analyses of data collected under Enanta Pharmaceuticals, Inc. Protocol EDP 305-102 entitled “*A Phase 2b Randomized, Double Blind, Placebo-Controlled, Multicenter Study Evaluating Safety and Efficacy of EDP-305 in Subjects with Liver Biopsy Proven NonAlcoholic Steatohepatitis (NASH)*”.

This SAP should be read in conjunction with the study protocol and case report form (CRF). This version of the plan has been developed using the protocol version 3.0 (Amendment 2.0) dated 21March2021. Any further changes to the protocol may necessitate updates to the SAP.

Any deviations from this SAP will be described and justified in the Clinical Study Report (CSR).

The preparation of this SAP has been based on International Conference on Harmonization (ICH) E9 guidelines. The table of contents and shells for the tables, figures and listings (TFLs) will be produced in a separate document. All data analyses and generation of TFLs will be performed using SAS 9.4® or higher.

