## **8 STATISTICAL METHODS**

### **8.1 General statistical conventions**

All statistical procedures will be completed using SAS version 9.4 or higher.

Unless otherwise stated, all statistical testing will be two-sided and will be performed using a significance (alpha) level of 0.05. Two-sided 95 % confidence intervals (CI) will be provided when relevant. Any p-value below 0.05 will be displayed to 4 decimal places.

Any p-value less than 0.0001 will be displayed as <0.0001. Any p-value between 0.05 (inclusive) and 0.10 will be displayed to 3 decimal places and any p-value greater than 0.10 will be displayed to two decimal places. Any p-value greater than 0.9999 will be displayed as >0.99.

All quantitative endpoints will be summarized using an 8-number summary (n, mean, standard deviation, median, 25th percentile, 75th percentile, minimum and maximum values). The mean and median and the percentiles will be rounded to one decimal place beyond the precision of the values being summarized, the standard deviation will be rounded to 2 additional decimal places beyond this precision and the minimum and maximum values will be displayed in the same precision. All qualitative endpoints will be summarized by the number of subjects meeting the endpoint and the percentage of subjects out of the appropriate population. The denominator will be displayed when needed and the percentage will be rounded to one decimal place

All subject data, including those derived, will be presented in individual subject data listings. Unless otherwise stated, unscheduled visit results will be included in date/time chronological order, within subject listings only. All listings will be sorted by investigational site, patient number, date/time, and visit. The treatment group as well as patient's sex and age will be stated on each listing. Unless otherwise stated, data listings will be based on all subjects randomized.

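### The treatment-emergent-high count in SAP 8.7.3 cannot include a subject whose fasting glucose starts above ULN, so it under-counts glucose worsening in a trial that enrols T2DM subjects

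*SAP*

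**What the plan says.** SAP 8.7.3 plans a by-arm number and percentage of subjects with treatment-emergent laboratory abnormalities up to the last dose. Where a test is continuous, the SAP rule reads: "Treatment-emergent high is defined as a change from a result less than or equal to the high limit at baseline to a value greater". The rest of that sentence compares the later value with the same limit. Protocol 11.7.3 gives the same definition. Under it, both documents place a reporting line: "Results will be reported according to any value greater than the high limit, any value greater than 2x ULN and 3x ULN".

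The other laboratory displays are:
- Continuous summaries: "Summaries of clinical laboratory values and change from baseline will be performed using an 8-number summary by visit and treatment group".
- Shift tables. SAP 8.7.3: "In addition, shift from baseline tables will be generated by visit and treatment group". Protocol synopsis: "Shift tables will also be generated for each safety laboratory parameter". The SAP does not define the shift categories; Protocol 11.7.3 says shifts are shown as "treatment-emergent abnormal, high, or low results".
- Listings with out-of-range values flagged.

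Neither section grades laboratory values. CTCAE grading appears for AEs (Protocol 9.2, SAP 8.7.1). SAP section 1 adds that "shells for the tables, figures and listings (TFLs) will be produced in a separate document"; that document was not available, so this point concerns the SAP text only.

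**The concern.** Glucose is an analyte with a known signal. Protocol 1.4.2 and 1.5.1 report Grade 3 glucose increases more often on EDP-305 than on placebo. Protocol 4.2.1 deliberately keeps T2DM patients in the trial, Protocol 5.6 stratifies on T2DM status, and the HbA1c exclusion begins only at 9.5%. Some subjects can be expected to start with fasting glucose above ULN, and the counting rule shuts them out.

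The plan handles raised or pre-existing states differently elsewhere. Its AE definition includes worsening (Protocol 11.7.2, SAP 8.7.1), and its ALT/AST stopping rules combine multiples of a subject's own reference baseline with multiples of ULN (SAP 8.7.2). Laboratory glucose has no comparable rule. At stake is whether a reader of the laboratory incidence table sees the full number of subjects whose glucose worsened, in a section that SAP section 9 leaves in place after the study's termination.

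**Working it through.** The plan states no figure for this point, so there is none to reproduce. The check applies the rule literally and then asks what the other displays supply.

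**Step 1: the rule.** A subject counts if baseline ≤ ULN and a post-baseline value > ULN. With ULN set to 1:

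| Baseline | Highest later value | Counted in SAP 8.7.3? | Counted if any rise in ULN tier counts? |
|---|---|---|---|
| 0.9 | 1.1 | yes | yes |
| 0.9 | 2.2 | yes | yes |
| 1.1 | 2.2 | no | yes (>ULN to >2x) |
| 1.5 | 3.2 | no | yes (>ULN to >3x) |
| 2.1 | 3.5 | no | yes (>2x to >3x) |

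A subject above ULN at baseline contributes 0 whatever the rise.

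**Step 2: the 2x and 3x ULN line.** It sits under the treatment-emergent-high definition. Read as tiers of that definition, it brings no excluded subject back. Its wording could also be read as covering every subject. It would then count the level reached, and its lowest tier would include anyone who started high and stayed high, so worsening would still not be separated out.

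**Step 3: the other displays.**
- The 8-number summaries give the upper quartile and maximum of value and change at each visit, but not how many subjects worsened over the period. New antidiabetic treatment, which Protocol 5.9.3 allows with exceptions, can lower later values.
- Shift tables count subjects by arm. If their categories follow the Protocol wording, a worsening subject who starts high stays in the same cell.
- HbA1c is scheduled at Screening, Baseline, Week 12 and Week 72, and no subject had completed Week 72 assessments at termination (SAP section 9).
- The concomitant diabetes-medication table (SAP 8.4.4) is by arm but covers continuing as well as new drugs.
- AEs cover worsening of a pre-existing event (Protocol 9.2.1, SAP 8.7.1) and are graded. A laboratory finding becomes an AE through the investigator's judgement of clinical significance (Protocol 8.4) or a need for treatment (Protocol 9.2.1).

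**Step 4: size, under assumption only.** Subjects who cannot enter the count = N × s, where s is the share starting above ULN. The documents do not give s.
- Planned arm, N = 112: 112 × 0.2 = 22.4; 112 × 0.4 = 44.8; 112 × 0.6 = 67.2.
- Interim Analysis 1, about 75/3 = 25 per arm if arms are equal: 5, 10 and 15.

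These are subjects outside the count, not subjects who worsen. For events, if a share e of them occurs in subjects starting above ULN, the same in both arms, a count restricted to baseline ≤ ULN keeps N × rate × (1 − e). Borrowing the phase 2 Grade 3 rates of 21% (2.5 mg) and 4% (placebo) for illustration:

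| e | Active | Placebo | Gap, points |
|---|---|---|---|
| 0 | 23.5 | 4.5 | 17 |
| 25% | 17.6 | 3.4 | 12.75 |
| 50% | 11.8 | 2.2 | 8.5 |
| 75% | 5.9 | 1.1 | 4.25 |
| 90% | 2.4 | 0.4 | 1.7 |

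At the 1 mg rate of 7% the full count is 7.8 v 4.5, falling to 5.9 v 3.4 at e = 25% and 0.8 v 0.4 at e = 90%. The 1.5 and 2 mg doses lie between those studied, and arms of 112 were planned, not realised.

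**The case against.** The best case for the plan is that little turns on this one table. Safety is descriptive with no tests, the individual laboratory stopping rules concern ALT and AST, and SAP and Protocol agree. Shift tables also count subjects by arm, including those who start high. If the 2x/3x ULN line covers all subjects, those reaching these levels are counted by arm, and since randomization is stratified by T2DM status, a difference in level reached would be informative. Worsening of pre-existing hyperglycaemia is within AE scope and is tabulated by severity, and diabetes medication has its own table.

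Much of this stands, and it limits the point in four ways.
- A reader might infer that the glucose signal would be missed. The documents do not support that: subjects with a normal baseline still count, and several displays can show part of the rest.
- A reader might infer that this is the only by-arm laboratory count, or that shift tables can show a worsening subject only as unchanged. By-arm shift tables are planned, and their categories are undefined in the SAP.
- A reader might extend the point to uric acid. Protocol 1.4.2 reports Grade 3 uric acid in 18%, 19% and 4%, but nothing shows that baseline uric acid is often above ULN. What remains there is a preference for grades.
- A reader might take the illustrative counts as an estimate. They rest on assumed shares, and T2DM status is not the same as fasting glucose above ULN.

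What the objection does not supply is a specified count, by arm, of subjects whose laboratory glucose worsened from a raised baseline.

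**Conclusion.** The point holds in a limited form. By its own definition, the treatment-emergent-high count omits every subject whose fasting glucose starts above ULN. That matters for glucose because T2DM subjects are enrolled and the sponsor has already reported a graded glucose signal. The consequence is an under-count in one table, partly offset elsewhere. Its size cannot be derived from the documents; it depends on the baseline distribution of glucose and on how events divide between normal and raised baselines. No alpha or power is affected. Two uncertainties remain: the intended reading of the 2x/3x ULN line, and the unseen table shells, which may specify more than the SAP does. This is a cheap improvement of low to moderate priority.

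**What to change.** In SAP 8.7.3, for fasting glucose:
- Count as treatment-emergent any subject whose worst post-baseline category is higher than the baseline category, whatever the baseline.
- Tabulate worst post-baseline against baseline category by arm and by T2DM stratum, through Week 12 and overall.
- State one set of numeric limits in the SAP. Use the grade limits of EDP 305-101 if the sponsor confirms them; otherwise use the existing >ULN, >2x ULN and >3x ULN tiers. A CTCAE reference alone is not enough, because Protocol 9.2 names version 5.0 and the SAP 8.7.1 link is to 4.03. The ULN tiers are coarse: a rise that stays between 1x and 2x ULN would still not count.
- State whether the 2x/3x ULN line applies to all subjects or only to those at or below ULN at baseline.

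The same table for uric acid is optional. The cost is SAP wording and one or two extra descriptive tables from data already collected. SAP section 9 cancels neither 8.7.3 nor Interim Analysis 1, so the tables fit the remaining reporting.

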### ***Subject Exclusion Criteria***

*Subjects will not be eligible to participate in the study if they meet any of the following criteria:*

1. Laboratory Screening results as indicated below:
  - Total white blood cells (WBC)  $< 3000$  cells/mm^3
  - Absolute neutrophil count (ANC)  $< 1500$  cells/mm^3
  - Platelet count  $< 140,000$ /mm^3
  - International Normalized Ratio, INR  $> 1.2$  (unless due to use of anticoagulants)
  - Estimated glomerular filtration rate (eGFR)  $< 60$  mL/min according to the Modification of Diet in Renal Disease (MDRD) equation
  - AST  $\geq 5 \times$  ULN
  - ALT  $\geq 5 \times$  ULN
  - ALP  $\geq 2 \times$  ULN

- Total bilirubin > 1.5 times ULN during Screening.  
*[Note: Patients with Gilbert's syndrome will be allowed following review by the Medical Monitor if they have a known history of Gilbert's syndrome with a normal direct bilirubin value and normal reticulocyte count.]*
- 2. Pregnant or nursing females.
- 3. MELD: Model for End-stage Liver Disease score >12.
- 4. Clinical or laboratory evidence of known chronic liver disease such as alcoholic liver disease, primary biliary cholangitis (PBC), primary sclerosing cholangitis (PSC), autoimmune hepatitis, Wilson disease, iron overload, alpha-1-antitrypsin deficiency, drug-induced liver injury, known or suspected hepatocellular carcinoma (HCC).
- 5. History of acute liver complications due to gallstones (e.g., acute cholecystitis or acute biliary obstruction), unless the subject has had a cholecystectomy (more than 12 weeks prior to Screening).
- 6. History of liver transplant, or current placement on a liver transplant list.
- 7. Hepatorenal syndrome (type I or II).
- 8. Prior variceal hemorrhage, uncontrolled encephalopathy, liver cirrhosis Child-Pugh Class A, B, and C, esophageal varices, or refractory ascites within the previous 26 weeks of Screening and/or histological presence of liver cirrhosis.
- 9. Prior or planned ileal resection, or prior or planned bariatric surgery. *[Note: Subjects who have undergone gastric surgeries that do not affect drug absorption (e.g., gastric band or gastric sleeve procedures) will be allowed if they are stable for at least 1 year prior to Screening. Gastrectomy or Roux-en-Y bypass will be allowed if stable for at least 3 years prior to Screening.]*

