### 9.2.1. Documenting and Reporting Adverse Events

All AEs regardless of the intensity, seriousness, or relationship to study drug will be reported from the time of informed consent to the end-of-study. AEs for each subject will be recorded in the subject's source documents and in the subject's AE eCRF and Clinical Trials SAE Form (if applicable).

Grade AEs (serious and non-serious) in accordance with the NCI/CTCAE scale (available at [https://evs.nci.nih.gov/ftp1/CTCAE/CTCAE\\_5.0\\_2010-06-14\\_QuickReference\\_8.5x11.pdf](https://evs.nci.nih.gov/ftp1/CTCAE/CTCAE_5.0_2010-06-14_QuickReference_8.5x11.pdf)) as presented below:

- **Mild** (Grade 1) asymptomatic or mild symptoms; clinical or diagnostic observations only; intervention not indicated
- **Moderate** (Grade 2) minimal, local or noninvasive intervention indicated; limiting age-appropriate instrumental activities of daily living
- **Severe** (Grade 3) Severe or medically significant but not immediately life-threatening; hospitalization or prolongation of hospitalization indicated; disabling; limiting self-care activities of daily living
- **Life-threatening** (Grade 4) Life-threatening consequences; urgent intervention indicated
- **Death** (Grade 5) Death related to the AE.

Any recurrence of an AE with similar causality to study drug will be reported as recurrence or exacerbation of the initial event, and not as a new event. Whenever possible, report AEs as a specific diagnosis or syndrome (e.g., flu syndrome) rather than as individual signs or symptoms. If no specific diagnosis or syndrome is identified, AEs should be reported as separate and individual events.

An AE includes the following:

- Progression or exacerbation of the subject's underlying disease. Clinical sequelae that result from disease progression, such as pleural effusion or small bowel obstruction, are reportable as AEs.
- Pre-existing event that increases in frequency or intensity
- Condition detected or diagnosed during the study period, even though it may have been present, in retrospect, prior to the first dose of study drug

- Laboratory abnormalities outside of normal limits and requiring therapeutic intervention
- An overdose of the study drug without any signs or symptoms – a calculated dose that exceeds its correct dose by 10% or more and is administered to the subject will be considered an overdose and documented as an AE. The following events **will not** be identified as AEs in this study:

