### 8.7.1 Adverse events

All Adverse Events (AEs) will be classified by Primary System Organ Class (SOC) and Preferred Term (PT) according to the Medical Dictionary for Regulatory Activities (MedDRA) Version 23.0 or higher. All subjects in the safety analysis set will be included in the summaries.

AEs will be classified as pre-treatment AEs and treatment emergent adverse events (TEAEs) and are defined as follows:

**Pre-treatment AE:** A pre-treatment event is any event that meets the criteria for an AE/SAE and occurs after the subject signs the ICF but before receiving the first administration of study drug.

**TEAE:** A TEAE is defined as an AE occurring or worsening on or after the first dose of study drug until the last dose of study drug.

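### The 2x and 3x LLN rows lie above the lower limit and cannot grade low values; the 2x and 3x ULN rows leave their baseline condition unstated

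*SAP*

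**What the plan says.** SAP 8.7.3 (Clinical laboratory evaluations) tabulates by arm the subjects who have treatment-emergent laboratory abnormalities. For continuous tests:

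- High: "Treatment-emergent high is defined as a change from a result less than or equal to the high limit at baseline" to a later value above that limit. The reporting rule that follows is "Results will be reported according to any value greater than the high limit, any value greater than 2x ULN and 3x ULN".
- Low: the mirror image, from a baseline at or above the lower limit to a later value below it. Results are reported by "any value less than the lower limit, any value less than 2x LLN and 3x LLN".

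Protocol 11.7.3 has the same definitions and tiers, and spells out LLN and ULN as the limits of the normal range. Neither document says whether the multiple-of-limit rows keep the baseline condition.

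Baseline is the last value before first dose (SAP Table 2 and 8.7.3). At screening, protocol 3.2 excludes ALT or AST only from 5x ULN and ALP only from 2x ULN. For bilirubin the exclusion is "Total bilirubin > 1.5 times ULN during Screening", with an allowance for Gilbert's syndrome. For adverse events, the SAP counts worsening explicitly: "A TEAE is defined as an AE occurring or worsening on or after the first dose of study drug" (8.7.1).

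SAP 8.7 plans no tests on safety data. The list in SAP section 9 of analyses dropped after the study was terminated does not include 8.7.3.

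**The concern.** A tiered table of low values should separate mild from marked falls. These tiers run the wrong way: each further cut-off is easier to meet than the one before. Falls in platelets or neutrophils, for example, would get no severity grading from these rows.

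On the high side the trial admits subjects with raised liver enzymes, so the baseline condition decides who can be counted. Unless the table shells settle it, two programmers could fill the 2x and 3x ULN rows differently from the same data, and a reader of the report could not tell which rule was used. Because the Week 72 efficacy analyses were cancelled, the safety tables are a main remaining output.

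**Working it through.** The plan gives no figure to reproduce. The check is on the logic of the cut-offs. All subject values and reference ranges below are assumptions, since the documents give no reference ranges.

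**Low side.** For LLN > 0, LLN < 2 x LLN < 3 x LLN, so any value below LLN is also below both multiples. (If LLN = 0 the three cut-offs coincide and the rows are empty.)

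Take six hypothetical subjects, as (baseline, later value) in LLN units with ULN = 2.5: (1.2, 1.3), (1.2, 0.9), (1.5, 0.6), (1.1, 0.4), (0.8, 0.5), (2.4, 2.3). *Nested* means the row keeps the treatment-emergent definition; *any value* means it does not.

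| Row | Nested | Any value |
|---|---|---|
| < LLN | 3 | 4 |
| < 2x LLN | 3 | 5 |
| < 3x LLN | 3 | 6 |
| for contrast: < 1/2 LLN | 1 | 1 |
| for contrast: < 1/3 LLN | 0 | 0 |

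Nested, the three planned rows are identical. Under the any-value reading they grow by adding normal results (1.3, then 2.3).

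The share of the normal range lying below k x LLN is (min(k x LLN, ULN) - LLN) / (ULN - LLN):

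| ULN/LLN | below 2x LLN | below 3x LLN |
|---|---|---|
| up to 2 | 100% | 100% |
| 3 | 50% | 100% |
| 4 | 33% | 67% |
| 5 | 25% | 50% |

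As an example, an assumed platelet LLN of 130,000 to 160,000/mm3 puts the 2x tier at 260,000 to 320,000 and the 3x tier at 390,000 to 480,000. A subject steady at 250,000 is below all of these. That subject is counted as low only under the any-value reading; under the nested reading the rows are merely redundant.

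**High side.** Let b be baseline and p the highest later value, both in ULN units, with cut-offs c = 2 and 3. A subject enters row c as follows:

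- nested: b <= 1 and p > c
- any value: p > c
- cut-off crossing: b <= c and p > c

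Number of the two rows (>2x, >3x ULN) in which each profile is counted:

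| b to p | Nested | Any value | Crossing |
|---|---|---|---|
| 0.9 to 3.5 | 2 | 2 | 2 |
| 1.5 to 3.5 | 0 | 2 | 2 |
| 2.5 to 3.5 | 0 | 2 | 1 |
| 3.5 to 3.5 | 0 | 2 | 0 |
| 3.5 to 4.9 | 0 | 2 | 0 |

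The first two readings disagree for all four profiles that start above ULN. The nested reading records a rise from a normal baseline correctly but omits every rise from an elevated one. The any-value reading gives an unchanged 3.5 the same count as a rise from 1.5 to 3.5.

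**Where the last profile would appear.** A rise from 3.5 to 4.9 is 4.9 / 3.5 = 1.4 times baseline and stays below 5x ULN. If Reference Baseline is near 3.5, it meets none of the ALT/AST stopping rules in SAP 8.7.2.

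**The case against.** The best defence is that the nested reading is the natural one. SAP 8.7.3 says the tables count treatment-emergent abnormalities, and each reporting line directly follows its definition. On that reading no normal value is called low, and moving from normal to abnormal is a usable emergence rule. Table shells are a separate document (SAP section 1) and may fix the row conditions.

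Other outputs also carry worsening. Change-from-baseline summaries and complete listings remain. Stopping-rule counts are planned ("Summaries will be provided using counts and percentages for subjects who meet the stopping rules as described below"). For ALT/AST the close-monitoring listing in SAP 8.7.2.1 would pick up the 1.5 to 3.5 profile if Reference Baseline is near 1.5, since 3.5 / 1.5 = 2.33 exceeds 2x and 3.5 exceeds 3x ULN.

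Most of this stands and limits the severity. It does not rescue the low rows: no shell can put 2x LLN below LLN, and the nested reading makes them duplicates. Nor does it supply the missing sentence on the high side.

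The other outputs should not be over-credited either. The protocol synopsis promises "Shift tables will also be generated for each safety laboratory parameter", but no category finer than normal/abnormal or high/low is stated, so a high-to-high shift could hide a rise. The stopping rules are triggered by ALT or AST. A laboratory change reaches the adverse event tables only if it is reported as an event, for example under "Laboratory abnormalities outside of normal limits and requiring therapeutic intervention" in protocol 9.2.1.

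**Conclusion.** The low-side tiers are wrong as written: two of three low rows carry no severity information for any analyte with LLN > 0, whichever reading is taken. The high-side rows lack a stated baseline condition. The nested reading measures emergence only from a normal baseline, and the any-value reading also counts unchanged elevations. Severity is minor, because the tables are descriptive and no hypothesis test depends on them. The low-side result needs only LLN > 0; the profiles and ranges above are illustrations.

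Three stronger conclusions might be inferred and are not supported:

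- That neither high-side reading measures emergence. A move from 0.9x to 3.5x ULN is emergent by the SAP's own definition, and the nested reading counts it in both rows. That reading is incomplete, not empty.
- That worsening from a raised baseline vanishes from the report. It is missing, under the nested reading, from these incidence tables; the values remain in the change-from-baseline summaries and listings.
- That the screening limits bound baseline, so that every subject is at or below 2x ULN for ALP and bilirubin. Baseline is the last pre-dose value, and under the protocol screening can begin up to 70 days before first dose. Bilirubin has the Gilbert's allowance. GGT, creatine kinase, lipase and triglycerides have no entry ceiling at all.

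**What to change.** 1. Replace 2x and 3x LLN with pre-stated reporting cut-offs below LLN. The sponsor should choose the fractions for each analyte, or keep the below-LLN row alone where the normal range is narrow.
2. For each high cut-off c (ULN, 2x ULN, 3x ULN), count a subject whose baseline is at or below c and who has any post-baseline value above c. Use as denominator the subjects at or below c at baseline, and print it. The numerator of the ULN row does not change. The same sentence in mirror image would settle the new low rows.
3. Footnote that subjects already above 3x ULN at baseline fall outside all three rows and that their values appear in the change-from-baseline summaries and listings. Do not state that shift tables, stopping-rule counts or adverse event tables capture their worsening.
4. Record the change in SAP section 9 if it is made before unblinding, since protocol 11.1 allows SAP changes only until then. Otherwise justify it in the clinical study report, as SAP section 1 provides. The documents do not say whether unblinding has occurred.

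The cost is SAP wording and minor table reprogramming, with no new data. Reported incidence may change in every arm; no direction is implied for the difference between arms.
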